#### **4.8. Comments**

All comments will be listed in one listing, indicating each domain.

### **5. EFFICACY EVALUATIONS**

Efficacy assessments will be performed at the planned time points indicated in section 2.3 above (see Appendix 4, 5 and 6) using the ITT population. All HBV virology (i.e. HBV DNA and RNA) and serology (i.e. HBsAG, HBeAg, HbcAg, Anti-HBs, Anti-HBe) available data will be analyzed by subject population, hepatitis B e antigen (HBeAg) status

---

and overall, treatment group, analysis phase, analysis period and follow-up type and at each analysis time point (when applicable). Placebo treatments can be pooled as ‘placebo’ over Parts A and B. The sections below describe the data handling rules used in the primary, secondary and exploratory analysis.

### **5.1. Data handling rules**

Units as provided in the SAP will be used in the analyses if these are deviated from the units provided in the Study Data Tabulation Model (SDTM) data. The viral activity parameters (i.e. virology and serology parameters) will be analyzed using log10 transformation rounded to 2 decimal places.

Historical as actual data for viral activity parameters will be used in the analysis. In the case a diluted and a non-diluted sample are present for a parameter at any time point, only the diluted sample will be included in the analysis. Historical viral activity measurements will not be imputed. The actual measurements will be imputed as follows:

- **HBsAg** values were tested with an upper limit of quantification of 124925.00 IU/mL and a lower limit of quantification of 0.05 IU/mL. Samples for the determination of HBsAg were processed in real-time using an assay such as the ARCHITECT platform (Abbott Laboratories).
  - Values above the upper limit of quantification (124925.00 IU/mL), will be imputed by the value of round (ULOQ+(ULOQ/10)) IU/mL in the analysis.
  - Values below the lower limit of quantification (0.05 IU/mL) will be imputed by a rounded value of (LLOQ/2) IU/mL in the analysis.
  
- **HBeAg** values were tested with an upper limit of quantification of 1400.00 IU/mL and a lower limit of quantification of 0.11 IU/mL.
  - Values above the upper limit of quantification (1400.00 IU/mL), will be imputed by a value of round (ULOQ+(ULOQ/10)) IU/mL in the analysis.
  - Values below the lower limit of quantification (0.11 IU/mL) will be imputed by a rounded value of (LLOQ/2) IU/mL in the analysis.

---

- **HBcrAg** values were tested within a measurement range of 3.0 LogU/mL - 9.0 LogU/mL
  - Values below lower limit of quantification (<3.0 LogU/mL) will be imputed by 2.7 log U/mL
  - Values above the upper limit of quantification (official ULOQ = 7 Log U/ml but with dilution ULOQ= 9.0 Log U/ml) will be imputed by value of round (ULOQ+(ULOQ/10)) log10U/mL with or without dilution method
- **Plasma HBV DNA** values were measured by the HBV COBAS AmpliPrep – COBAS TaqMan, V. 2.0 test (lower limit of quantification 20 IU/mL). Values below the lower limit of quantification (20 IU/mL) will be imputed as follows:
  - Values below the lower limit of quantification (20 IU/mL), but target detected will be imputed by a value of 15 IU/mL in the analysis.
  - Values below the lower limit of quantification (20 IU/mL, target not detected) will be imputed by a value of 5 IU/mL in the analysis.
  - Values above the upper limit of quantification (>170000000 IU/mL), will be imputed by the value of round (ULOQ+(ULOQ/10)) IU/mL in the analysis
- **HBV RNA** values were tested with an upper limit of quantification (ULOQ) and a lower limit of quantification (LLOQ), all values, even below LLOQ (4.0 log10 cp/mL) or LOD (2.49 log10 cp/mL) will be reported and all numeric values will be used in the analysis.
  - Negative or Not Detected (“TND”) values will be imputed by a value of 5 copies/mL ( $\log_{10}(5) = 0.69897$  log10 cp/mL) in the analysis.
  - Values above the upper limit of quantification (>ULOQ), will be imputed by the value of round (ULOQ+(ULOQ/10))  $\log_{10}$  cp/mL in the analysis
- **Anti-HBs** values were tested with an upper limit of quantification (ULOQ) and lower limit of quantification (LLOQ), all values, even below LLOQ (< 5.0 mIU/mL) will be reported and all numeric values will be used in the analysis.

---

- Values below LLOQ (<5mIU/mL) will be imputed by value of round (LLOQ/2) mIU/mL
- Values “>10000.00 mIU/mL” (with annotation “diluted for quantitation”) will be imputed by value of round (ULOQ+(ULOQ/10)) mIU/mL

Additionally, all other viral activity data with values below a LLOQ and not included in the imputation rules above will be imputed by the absolute value divided by 2 and rounded to the amount of decimal place provided in the dataset.

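### HBcrAg values above the upper limit of quantification are raised by 10% on the log10 scale (+0.70 or +0.90 log10), so anyone later measured at or below that limit is scored as a >0.5 log10 reduction

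*SAP*

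**What the plan says.** SAP 5.1 (Data handling rules) uses one formula for results above the ULOQ: the limit plus one tenth of the limit, rounded.

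- **HBsAg:** "Values above the upper limit of quantification (124925.00 IU/mL), will be imputed by the value of round (ULOQ+(ULOQ/10)) IU/mL in the analysis".
- **HBeAg:** "Values above the upper limit of quantification (1400.00 IU/mL), will be imputed by a value of round (ULOQ+(ULOQ/10)) IU/mL in the analysis". HBV DNA and anti-HBs follow the same pattern, also in linear units.
- **HBcrAg:** the limit is given as "official ULOQ = 7 Log U/ml but with dilution ULOQ= 9.0 Log U/ml", and a result above it "will be imputed by value of round (ULOQ+(ULOQ/10)) log10U/mL with or without dilution method".
- **HBV RNA:** "Values above the upper limit of quantification (>ULOQ), will be imputed by the value of round (ULOQ+(ULOQ/10", with the result in log10 cp/mL. The assay description gives an LLOQ and a detection limit but no number for the ULOQ: "values were tested with an upper limit of quantification (ULOQ) and a lower limit of quantification (LLOQ), all values, even below LLOQ (4.0 log10 cp/mL".

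Viral activity parameters "will be analyzed using log10 transformation rounded to 2 decimal places". The precision of the round function inside the formula is not stated.

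SAP Table 4 (section 5.3) has a single HBcrAg reduction category, more than 0.5 log10 from baseline, although the text of that row names HBV DNA. One qualifying visit is enough for a subject to count for a whole phase or period. The HBV RNA reduction categories are >1, >2 and >3 log10.

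**The concern.** Adding 10% to a concentration is a small nudge above the limit. Adding 10% to the logarithm of a concentration is a multi-fold jump. The formula appears to have been carried from the assays reported in linear units to two assays reported in log units, with no stated reason for a much larger step there.

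The artificial step is larger than the response threshold applied to the same marker. A subject whose HBcrAg barely moves across the ULOQ would be reported as a responder, and the change-from-baseline and maximum-decrease summaries would carry the same step. Arms are small (planned 10 on placebo+NA and 30 on JNJ-56136379+NA per population and part, protocol 3.1), so one such subject moves a proportion by 1/10 = 10 or 1/30 = 3.3 percentage points.

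**Working it through.** The SAP prints no imputed above-ULOQ value, so there is no planned figure to reproduce. The one conversion printed in SAP 5.1, log10(5) = 0.69897, is correct.

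**Formulas.** Imputed value = ULOQ + ULOQ/10, in the unit the SAP gives. Shift = imputed minus ULOQ on the log10 scale. Fold = 10^shift.

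**Markers in linear units**
- HBsAg: 124925 becomes 137418 IU/mL; log10(137418/124925) = 0.041.
- HBeAg: 1400 becomes 1540 IU/mL; log10(1.1) = 0.041.
- HBV DNA: 170000000 becomes 187000000 IU/mL; log10(1.1) = 0.041.

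**HBcrAg, in log units**
- Undiluted: 7 + 0.7 = 7.70; shift 0.70; 10^0.70 = 5.01-fold.
- Diluted: 9 + 0.9 = 9.90; shift 0.90; 10^0.90 = 7.94-fold.
- If the round function means nearest integer: 8 and 10; shift 1.0 in both cases, 10-fold.

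**Effect on the >0.5 log10 category**
- Baseline above 7, later measured at 7.0 or lower: scored fall at least 7.70 - 7.0 = 0.70, always above 0.5.
- Baseline above 9.0, later measured at 9.0 or lower: scored fall at least 9.90 - 9.0 = 0.90, always above 0.5.
- A true fall from 7.1 to 7.0 is 0.1 but is scored as 0.70.
- The distortion also runs upward: a true rise from 6.9 to 7.1 is 0.2, but if the second result is reported as above 7 it is scored as 7.70 - 6.9 = 0.80.
- Both visits above the same ULOQ: scored change 0.

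**With the 10% applied before log10**
- log10(1.1 x 10^7) = 7.04 and log10(1.1 x 10^9) = 9.04.
- A baseline above 7 then counts as a >0.5 reduction only if the later value is below 7.04 - 0.5 = 6.54; a baseline above 9.0, only if it is below 9.04 - 0.5 = 8.54.

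**HBV RNA, ULOQ not given.** Reading the limit in log10 cp/mL, as the result unit implies, the shift is ULOQ/10. Because the LLOQ is 4.0, the ULOQ must be higher, so the shift exceeds 0.4 log10 (10^0.4 = 2.5-fold). Over assumed limits:
- ULOQ 5: +0.5 (3.2-fold).
- ULOQ 7: +0.7 (5.0-fold).
- ULOQ 9: +0.9 (7.9-fold).
- ULOQ 11: +1.1 (12.6-fold).

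With 2-decimal rounding, the shift alone passes the lowest RNA category (>1 log10) only if the ULOQ is above 10.

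**The case against.** A result above the ULOQ is censored. An undiluted reading above 7 could lie anywhere up to 9 on the SAP's own range, so 7.7 may be too low as easily as too high, and 7.04 would understate the decline of a subject who started well above the limit. A deliberate log-scale rule cannot be excluded: the lower-end HBcrAg imputation of 2.7 equals 3.0 minus 10% on the log scale, as well as half the limit on the linear scale (log10 500 = 2.70). This stands as a caution that no single imputed value is right. It does not justify a rule whose scale conflicts with the other markers and which fixes responder status for everyone who drops to or below the limit.

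The plan already uses the diluted result when both exist at a time point, and dilution measures values between 7 and 9. The 7.7 imputation therefore touches only samples left undiluted. The precedence rule works within a time point and does not align visits, and neither document says how often a sample stays undiluted.

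The reach is also limited. The protocol treats HBcrAg as exploratory and descriptive; SAP 5.3 lists it as secondary and SAP 5.5 as exploratory. HBcrAg reduction is not among the proportions listed for between-arm comparison, and HBcrAg has no row in the time-to-event table. No formal hypothesis testing is planned.

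**Conclusion.** The scale error holds for HBcrAg as the rule is written: +0.70 or +0.90 log10 in place of +0.04, with certain entry into the >0.5 log10 category when baseline is above the ULOQ and a later value is at or below it. This assumes 2-decimal rounding; integer rounding would make both steps 1.0 log10. The number of subjects affected is unknown, and the effect is confined to secondary and exploratory outputs. The primary HBsAg endpoint is not affected.

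Two stronger readings do not follow from the documents.

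- A reader might infer that HBV RNA suffers the same 5- to 8-fold jump and the same false responders. The scale inconsistency is there, but no RNA ULOQ is given, so only a shift above 0.4 log10 can be stated. RNA has no >0.5 category, and the phase 1 summary in protocol 1.1 describes baseline RNA as generally low, so readings above the limit may be uncommon.
- A reader might infer that the bias falls mainly on HBeAg-positive subjects. Neither document gives HBcrAg levels by HBeAg status or counts above the ULOQ. By construction it falls on those with the highest HBcrAg; more cannot be said.

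**What to change.** In SAP 5.1, state that for HBcrAg and HBV RNA the 10% is applied on the linear scale before log10, so that the imputed value is log10(ULOQ) + 0.04, rounded to 2 decimals: 7.04 or 9.04 for HBcrAg, and likewise for HBV RNA. Give the HBV RNA ULOQ. In Table 4, replace HBV DNA with HBcrAg in the text of the HBcrAg response and reduction rows.

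The cost is a few lines of SAP text and one derivation step for each of two assays. Data collection does not change. Any interim HBcrAg or HBV RNA output already produced under the current rule would need to be rerun.

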### ***Antiviral Activity***

Antiviral activity is examined in the ongoing Part 2 of study 56136379HPB1001 (Sessions 8 to 11), in CHB-infected subjects.

Interim data from the 25- to 250-mg dose show that JNJ-56136379 administration leads to reduction in HBV DNA. A mean ( $\pm SD$ ) reduction in plasma HBV DNA levels of 2.16 (0.49)  $\log_{10}$  IU/mL (25 mg), 2.89 (0.48)  $\log_{10}$  IU/mL (75 mg), 2.70 (0.53)  $\log_{10}$  IU/mL (150 mg), and 2.70 (0.33)  $\log_{10}$  IU/mL (250 mg) from baseline was observed at Day 29. In the 250-mg dosing group, 5 out of 12 subjects achieved HBV DNA levels below the LLOQ of the HBV DNA assay, while 3 out of 12 subjects in both the 75-mg and 150-mg dosing groups and none (out of 12) of the subjects in the 25-mg dosing group achieved this.

A more pronounced and consistent decline in HBV DNA levels was observed across subjects in the 75-mg, 150-mg, and 250-mg group compared with the 25-mg group.

HBV RNA was assessed as an exploratory endpoint using a validated research assay. In line with HBV DNA levels, reductions in HBV RNA levels were observed with JNJ-56136379 treatment. Baseline levels of HBV RNA were generally low and in some instances undetectable, especially in the higher dose groups, limiting the HBV RNA decline observable in this study.

No notable changes in HBsAg or HBeAg were observed.

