**Table 4: response categories for viral activity parameters**

	Category criteria	Additional info
HBsAg Response	Subject who has achieved a HbsAg level <1000 IU/mL per time point	These proportions will also be included per analysis phase and analysis period. A subject will be included in the numerator if the response category is at least once met within the analysis phase/period.
	Subject who has achieved a HbsAg level <100 IU/mL per time point	
	Subject who has achieved a HbsAg level <10 IU/mL per time point	
	Subject who has achieved a HbsAg level <0.05 IU/mL per time point	
HBV DNA Response	Subject who has achieved a HBV DNA level <1 log10 IU/mL per time point	These proportions will also be included per analysis phase and analysis period. A subject will be included in the numerator if the response category is at least once met within the analysis phase/period.
	Subject who has achieved a HBV DNA level <2 log10 IU/mL per time point	
	Subject who has achieved a HBV DNA level <3 log10 IU/mL per time point	
	Subject who has achieved a HBV DNA level <20 IU/mL per time point	
	Subject who has achieved a HBV DNA level <60 IU/mL per time point	
	Subject who has achieved a HBV DNA level <100 IU/mL per time point	
	Subject who has achieved a HBV DNA level <1000 IU/mL per time point	
	Subject who has achieved a HBV DNA level <2000 IU/mL per time point	
	Subject who has achieved a HBV DNA level <20000 IU/mL per time point	
	Subject who has achieved a HBV DNA level < LLQ for target detected and not detected per time point	
	Subject who has achieved a HBV DNA level < LLQ for target not detected per time point	
	Subject who has achieved a HBV DNA level < LLQ for target detected per time point	
HBV RNA Response	Subject who has achieved a HBV RNA level <100 cp/mL per time point	These proportions will also be included per analysis phase and analysis period. A subject will be included in the numerator if the response category is at least once met within the analysis phase/period.
	Subject who has achieved a HBV RNA level <1000 cp/mL per time point	
	Subject who has achieved a HBV RNA level <2000 cp/mL per time point	
	Subject who has achieved a HBV RNA level <20000 cp/mL per time point	
	Subject who has achieved HBV RNA target not detected per time point	
	Subject who has achieved HBV RNA < LLOQ per time point	
	Subject who has achieved a HBV RNA level <250 cp/mL at week 24	

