HbcrAg Response	Subject who has achieved a HBV DNA level <2 log10 IU/mL per time point	These proportions will also be included per analysis phase and analysis period. A subject will be included in the numerator if the response category is at least once met within the analysis phase/period.
	Subject who has achieved a HBV DNA level <3 log10 IU/mL per time point	
	Subject who has achieved a HBV DNA level $\geq 2 - < 3$ log10 IU/mL per time point	
HbsAg Reduction	Subject who has HbsAg reduced by > 0.3 log10 IU/mL from baseline per time point	These proportions will also be included per analysis phase and analysis period. A subject will be included in the numerator if the response category is at least once met within the analysis phase/period.
	Subject who has HbsAg reduced by > 0.5 log10 IU/mL from baseline per time point	
	Subject who has HbsAg reduced by > 1 log10 IU/mL from baseline per time point	
	Subject who has HbsAg reduced by > 2 log10 IU/mL from baseline per time point	
	Subject who has HbsAg reduced by > 3 log10 IU/mL from baseline per time point	
HbeAg Reduction	Subject who has HbeAg reduced by > 0.5 log10 IU/mL from baseline per time point	These proportions will also be included per analysis phase and analysis period. A subject will be included in the numerator if the response category is at least once met within the analysis phase/period.
	Subject who has HbeAg reduced by > 1 log10 IU/mL from baseline per time point	
	Subject who has HbeAg reduced by > 2 log10 IU/mL from baseline per time point	
HBV DNA Reduction	Subject who has HBV DNA reduced by > 1 log10 IU/mL from baseline per time point	These proportions will also be included per analysis phase and analysis period.

	Subject who has HBV DNA reduced by $> 2 \log_{10}$ IU/mL from baseline per time point	A subject will be included in the numerator if the response category is at least once met within the analysis phase/period.
	Subject who has HBV DNA reduced by $> 3 \log_{10}$ IU/mL from baseline per time point	
	Subject who has HBV DNA reduced by $> 1 \log_{10}$ IU/mL from baseline at week 4 and confirmation at week 8.	
HBV RNA Reduction	Subject who has HBV RNA reduced by $> 1 \log_{10}$ cp/mL from baseline per time point	These proportions will also be included per analysis phase and analysis period. A subject will be included in the numerator if the response category is at least once met within the analysis phase/period.

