	Subject who has HBV RNA reduced by $> 2 \log_{10}$ cp/mL from baseline per time point	
	Subject who has HBV RNA reduced by $> 3 \log_{10}$ cp/mL from baseline per time point	
HbcrAg Reduction	Subject who has HBV DNA reduced by $> 0.5 \log_{10}$ IU/mL from baseline	These proportions will also be included per analysis phase and analysis period. A subject will be included in the numerator if the response category is at least once met within the analysis phase/period.

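### HBV RNA not detected is imputed 1.79 log10 below the assay's stated limit of detection, so subjects with unquantifiable baselines can be scored as >1, >2 or >3 log10 RNA responders

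*SAP*

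**What the plan says.** SAP Section 5.1 states both assay limits for HBV RNA and keeps every number the assay returns: "all values, even below LLOQ (4.0 log10 cp/mL) or LOD (2.49 log10 cp/mL) will be reported and all numeric values will be used". Results reported as negative or not detected have no number, and for these the rule is that "values will be imputed by a value of 5 copies/mL". Viral markers "will be analyzed using log10 transformation rounded to 2 decimal places".

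The imputed value then enters several outputs:

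- SAP Table 4 has an HBV RNA reduction block, whose rows begin "Subject who has HBV RNA reduced by" and set thresholds of >1, >2 and >3 log10 from baseline. They are counted per time point and also per analysis phase or period, where meeting the criterion once is enough.
- SAP Table 5 defines time to each of these reductions.
- SAP Section 5.3 lists the proportion with HBV RNA reduction among the secondary categorical endpoints and includes RNA in the maximum decrease from baseline.
- SAP Section 5.5 covers RNA change from baseline, with a mixed model to compare treatments.

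Table 4 also has absolute response rows for RNA, including <100 copies/mL and "Subject who has achieved a HBV RNA level <250 cp/mL at week 24". Not detected and <LLOQ have rows of their own.

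The protocol lists HBV RNA as an exploratory endpoint (Section 2.1), to be analysed descriptively (Section 11.3.3). On the Phase 1 experience, Section 1.1 reports: "Baseline levels of HBV RNA were generally low and in some instances undetectable, especially in the higher dose groups".

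**The concern.** A constant that stands in for an undetectable result should sit close to what the assay can resolve. Here it sits far below, so a change from detectable to not detected is scored as a large fall, most of which the assay could not have measured. The responder categories then partly reflect the chosen constant rather than the drug.

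Low baselines are the most exposed, and Phase 1 suggests they will be common. HBV RNA is also close to the drug's stated mechanism, so readers will look at these outputs. If not-detected results turn out to be more frequent in the active arms, the constant would enlarge the apparent difference from placebo+NA.

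**Working it through.** **Inputs.** All from SAP Section 5.1: imputed value 5 copies/mL, LOD 2.49 log10, LLOQ 4.0 log10.

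**The plan's own figure.** log10(5) = 0.69897, as the SAP states; 0.70 after rounding to two decimals.

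**Distances.**

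- To the LOD: 2.49 − 0.70 = 1.79 log10 (10^1.79, about 62-fold; the LOD is 10^2.49 = 309 copies/mL).
- To the LLOQ: 4.0 − 0.70 = 3.30 log10.

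Gaps below the LLOQ for other markers in the same section: HBV DNA not detected, log10(20/5) = 0.60; HBsAg and HBeAg at LLOQ/2, about 0.30; HBcrAg, 3.0 − 2.7 = 0.30.

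**Baseline needed to be a responder at a not-detected visit.** For a threshold of k log10, the baseline must exceed the imputed value + k. The smallest fall to the LOD that goes with it is max(0, imputed value + k − 2.49).

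| Threshold | SAP rule (0.70) | Smallest fall to LOD | Floor at LOD/2 (2.19) | Floor at LOD (2.49) |
|---|---|---|---|---|
| >1 log10 | 1.70 | 0 | 3.19 | 3.49 |
| >2 log10 | 2.70 | 0.21 | 4.19 | 4.49 |
| >3 log10 | 3.70 | 1.21 | 5.19 | 5.49 |

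All three baselines under the SAP rule lie below the LLOQ, and the first lies below the LOD. Compared with a floor at the LOD, responder status at a not-detected visit depends only on the constant for baselines of 1.70 to 3.49 (>1), 2.70 to 4.49 (>2) and 3.70 to 5.49 (>3) log10.

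**Scored fall against fall to the LOD, for a subject who becomes not detected.**

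| Baseline (log10) | Scored | To LOD |
|---|---|---|
| 2.49 | 1.79 | 0.00 |
| 3.00 | 2.30 | 0.51 |
| 3.50 | 2.80 | 1.01 |
| 4.00 | 3.30 | 1.51 |

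**Means.** Each 10 percentage points of not-detected results at a visit moves an arm's mean RNA by 0.10 × (2.19 − 0.70) = 0.15 log10 relative to LOD/2, or 0.10 × 1.79 = 0.18 relative to the LOD. This counts the not-detected readings only.

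**The once-is-enough rule.** Take a subject with stable RNA at the LOD and a chance p, independent across visits, of a not-detected result at each visit. The documents give no p, so this is an assumed range. The chance of at least one false >1 log10 response is 1 − (1 − p)^n. For p = 2%, 5% and 10% it is 15%, 34% and 57% over the 8 scheduled visits to Week 24, and 25%, 51% and 77% over the 14 to Week 48. The protocol allows RNA to be tested on selected samples only, which would lower n.

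**The case against.** The best defence is that not detected does not mean the same as below the LOD in this SAP. Numeric readings under the LOD are kept, so not detected is a separate state that should rank below them, and a value under the LOD preserves that order. This stands. It rules out simply moving not-detected results up to the LOD while leaving sub-LOD numbers in place. It does not justify a constant 1.79 log10 down, and the SAP gives no reason for it.

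The comparison with other markers is also loose. RNA is not truncated at its LLOQ as HBV DNA is, no LOD is given for HBV DNA, and the SAP's halving rule applies only to markers without their own rule. The distance to RNA's own LOD therefore carries the argument.

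The consequences are limited as well. RNA is exploratory in the protocol, no formal hypothesis test is planned, and not detected is tabulated and timed separately, so a reader can see how common it is. That separate row does not correct the means, reduction categories or time-to-reduction outputs.

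A reader might go further and infer any of the following, none of which the documents support:

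- *The imputation alone creates >2 and >3 log10 responders.* The step below the LOD is 1.79, less than 2, so falls to the LOD of at least 0.21 and 1.21 are also needed.
- *Every detectable subject who becomes not detected is a >1 log10 responder.* A retained numeric baseline at or below 1.70 log10 does not qualify.
- *The <100 and <250 copies/mL rows merely repeat not detected.* They also catch numeric sub-LOD readings, whose frequency is not given.
- *The rule favours the drug.* No not-detected rates by arm are given. Subjects not detected at baseline start at 0.70, cannot decline, and show a rise of 1.79 if RNA returns to the LOD.

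**Conclusion.** The point holds. The SAP's rule adds up to 1.79 log10 of decline below the LOD to a not-detected visit. That is enough by itself for >1 log10 from a baseline at the LOD, and it admits baselines above 2.70 and 3.70 log10, neither quantifiable, to the >2 and >3 log10 categories at a single visit. The only sensitivity analysis in SAP Section 5.2.1.3 concerns HBsAg, so nothing planned would show how far RNA results depend on the constant.

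These thresholds follow from the SAP's own figures. How many subjects are affected, and whether arms differ, depends on the baseline RNA distribution and not-detected rates in this trial, which the documents do not give. The Phase 1 description of low baselines makes an effect plausible, but the protocol does not say that assay had the same limits. The consequence is confined to HBV RNA outputs. It should be corrected before those are reported, but it does not touch the primary analysis.

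**What to change.** In SAP Section 5.1, set both not-detected results and numeric readings below the LOD to one common assay-based floor, for example the LOD (2.49 log10) or LOD/2 (2.19 log10). Not detected then never ranks above a detected reading.

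In Tables 4 and 5, report each >k log10 RNA reduction, and the time to it, only among subjects whose baseline exceeds that same floor by more than k. Apply this to the denominator as well as the numerator; otherwise low-baseline subjects become automatic non-responders.

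Merge the <100 copies/mL (2.00 log10) and <250 copies/mL (2.40 log10) categories, which lie below the LOD, into a single category of below LOD or not detected. Keep the current rule, 5 copies/mL with all numeric readings, as a sensitivity analysis.

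The cost is SAP wording and minor dataset code, with no new data. Some RNA declines and responder rates will become smaller, fewer subjects will be evaluable for the >2 and >3 log10 categories, and sub-LOD readings will no longer contribute to the main RNA summary.
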